7.1 Definitions

7.1.1 Adverse Event (AE)

An adverse event (AE) is any untoward medical occurrence associated with the use of a drug in humans, whether or not considered drug related. An AE can be any unfavorable and unintended sign (including an abnormal laboratory finding), symptom or disease temporally associated with the use of a drug, without any judgment about causality.

7.1.2 Serious adverse Event (SAE)

A serious adverse event (SAE) is any adverse event, regardless of causality, that results in ANY of the following outcomes:

1. Death
2. A life-threatening adverse event
3. Inpatient hospitalization or prolongation of existing hospitalization for ≥ 24 hours
4. A persistent or significant incapacity or substantial disruption of the ability to conduct normal life functions
5. A congenital anomaly/birth defect.
6. Important Medical Events (IME) that may not result in death, be life threatening, or require hospitalization may be considered serious when, based upon medical judgment, they may jeopardize the patient or subject and may require medical or surgical intervention to prevent one of the outcomes listed in this definition (FDA, 21 CFR 312.32; ICH E2A and ICH E6).

7.2 Adverse Event List for BVD-523

In the following sections a short summary of preclinical data is provided. Detailed information is presented in the BVD-523 Investigator's Brochure.

Events Not Considered SAEs:

- Previously planned surgeries (prior to signing the ICF)
- Non-disease related elective surgeries
- Pre-planned hospitalizations or procedures for pre-existing conditions
- Death due to disease progression

Preliminary evidence from *in vitro* and *in vivo* toxicological assessments of BVD-523 suggests the molecule has a safety profile supportive of its development as an anti-cancer therapeutic. Additionally, human clinical trials have been conducted using other drugs known to affect the MAPK pathway and findings from these studies may provide information regarding possible safety risks that are mechanistically attributable to MAPK pathway inhibition.

Thus, BVD-523's risk profile may potentially include the following:

Dermatological Lesions

Dermatological lesions have been seen in rodent GLP toxicology studies of BVD-523. Several of the following findings displayed exposure-dependent increases in incidence and/or severity: non-specific dermal inflammation, pustular dermatitis, epidermal ulceration and acanthosis. These toxicities appeared to be associated with predominantly reversible pharmacodynamics, as the majority of findings were mild and/or of low incidence in animals that underwent dose cessation.

In clinical studies, other drugs that inhibit components of the MAPK pathway exhibit cutaneous toxicity. Multiple investigational inhibitors of MEK1/2 kinases exhibit exposure dependent, dose-limiting and reversible skin toxicities in a proportion of patients. Specific toxicities include: non-specific rash and pruritus, acneiform dermatitis, epidermal fissure and paronychia. Additionally, clinical experience with both investigational agents and approved drugs that primarily target BRAF kinase have displayed exposure-dependent and reversible skin toxicities in a proportion of treated patients; relevant lesions here include keratoacanthoma-type squamous cell carcinomas, non-cancerous hyperkeratosis and actinic keratosis.

A similar pattern of cutaneous toxicity was observed in the first 18 patients in the FIM Phase 1 study BVD-523-01, with two thirds of patients experiencing rash and 1 patient with a history of squamous cell carcinoma developing a squamous cell carcinoma while on treatment with BVD-523. Rash has been treated with topical or oral agents, and dose reductions/interruptions as needed. Patients in this study of BVD-523 will be monitored for signs of dermatological toxicities.

Phototoxicity

BVD-523 exhibits an absorbance peak in the range of UV-A/UV-B light, specifically at ~320 nM. Clinical studies of other drugs that modulate MAPK pathway components have exhibited skin phototoxicity, and photosensitization has been reported in 1 patient on a low dose of BVD-523 (20 mg b.i.d) in the FIM Phase 1 study.

Beyond dermatological monitoring (above), potential risks of direct phototoxicities induced by BVD-523 should be further minimized by advising that patients minimize sun exposure, use broad-spectrum sunscreens, and wear sunglasses. Patients should be informed that relevant sun exposure may occur even through glass, such as while driving.

Ophthalmological Effects

Preclinical toxicology studies of BVD-523 have not revealed any exposure-dependent ophthalmological toxicities; however, clinical studies of MEK1/2 kinase inhibitors highlight ocular toxicities that may reflect mechanistically attributable risks observable in a proportion of patients. Of particular concern are the following dose-limiting toxicities comprising exposure-dependent, serious adverse events during clinical studies: retinal vein occlusion, retinal detachment and related vision abnormalities. In the ongoing FIM Phase 1 study to date (1st April 2014) a single AE of vision changes has been reported in 1 patient on a low dose of BVD-523 (20 mg b.i.d). While it is not definitively understood whether ocular toxicities reflect primary pharmacology associated with global inhibition of the MAPK pathway specific management and exclusion criteria are defined in this clinical protocol.

Gastrointestinal Toxicity

Preclinical toxicity studies of BVD-523 provided evidence of exposure-related, reversible gastrointestinal toxicities, and these toxicities have also been observed at high frequency if the first 18 patients in the ongoing FIM Phase 1 study, in one case leading to an SAE of renal insufficiency secondary to dehydration. The severity and reversibility of these nonclinical and clinical toxicities, while not meriting a specific monitoring or treatment plan, warrant

active routine monitoring of patients for this toxicity.

QTc Prolongation

The balance of preclinical evidence suggests BVD-523 has low, but observable, potential to cause QT prolongation. Given potentially unique species sensitivity, as well as possibly unknown consequences following chronic dosing, patients dosed with BVD-523 are being monitored for potential QTc prolongation and any other related cardiotoxicities, including 12 hour Holter monitoring after the 1st and 3rd dose. No cardiac AEs have been reported in the first 18 patients treated with BVD-523 in doses up to 900 mg BID.

Tissue Mineralization

Tissue mineralization has been observed in rodent toxicology studies of BVD-523. The incidence and severity of mineralization was dose-dependent, and effects were observed in 1 or more tissues at toxic doses. In animals in which mineralization occurred after treatment with BVD-523, significantly increased serum phosphorus and modestly decreased serum calcium was seen; these effects were not observed in animals in which there was no mineralization.

Tissue mineralization has been reported in rodents with other compounds that target the MAPK pathway and published studies suggest that the MAPK pathway is a negative regulator of matrix mineralization both *in vitro* and *in vivo*.

Routine clinical laboratory tests, including blood chemistry analyses for calcium and inorganic phosphate, will be performed and any indication of abnormalities may result in further investigations. A clinical monitoring strategy similar to this was previously employed for related drugs that target the MAPK pathway.

Hematological Effects

Hematological effects observed in a rat repeat dose study included lowered reticulocyte counts, mean corpuscular volume, platelet counts (in females only) and increased neutrophil, monocyte, basophil and large unstained cell counts. In dogs the clinical pathology findings were consistent with inflammation (increased white blood cell count, neutrophils, fibrinogen and globulin) and decreased albumin and hemorrhage (decreased red cell mass).

In order to monitor for potential hematologic toxicity in humans, routine clinical laboratory hematology tests, should be performed and any indication of abnormalities may result in further investigations.

7.3 Adverse Event Characteristics

- **CTCAE term (AE description) and grade:** The descriptions and grading scales found in the revised NCI Common Terminology Criteria for Adverse Events (CTCAE) version 5.0 will be utilized for AE reporting. All appropriate treatment areas should have access to a copy of the CTCAE version 5.0. A copy of the CTCAE version 5.0 can be downloaded from the CTEP web site http://ctep.cancer.gov/protocolDevelopment/electronic_applications/ctc.htm.

- **For expedited reporting purposes only:**
 - AEs for the agent(s) that are listed above should be reported only if the adverse event varies in nature, intensity or frequency from the expected toxicity information which is provided.
 - Other AEs for the protocol that do not require expedited reporting are outlined in the next section (Expedited Adverse Event Reporting) under the sub-heading of Protocol-Specific Expedited Adverse Event Reporting Exclusions.

- **Attribution of the AE:**
 - Definite – The AE *is clearly related* to the study treatment.
 - Probable – The AE *is likely related* to the study treatment.
 - Possible – The AE *may be related* to the study treatment.
 - Unlikely – The AE *is doubtfully related* to the study treatment.
 - Unrelated – The AE *is clearly NOT related* to the study treatment.

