7.4 Expedited Adverse Event Reporting

7.4.1 Investigators **must** report to the Overall PI any serious adverse event (SAE) that occurs after the first dose of study treatment, during treatment, or within 30 days of the last dose of treatment on the local institutional SAE form. Study personnel must alert the Overall PI as soon as possible (**no later than 24 hours of the investigator learning of the SAE**).

7.4.2 Any serious adverse event (SAE) that occurs after the first dose of study treatment, during treatment, or within 30 days of the last dose of treatment should also be reported to BVD via Clinipace using the local institutional SAE form. Please include [name] ([contact]), [name] ([contact]) and [name] ([contact]) on all emails that are sent to Clinipace ([contact]) regarding SAEs.

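### Section 7.3 filters expedited reports of listed events by expectedness without exempting serious ones, while 7.4.1 and 7.4.2 require every SAE to be reported, so the two must be reconciled

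*Combined protocol and SAP*

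**What the plan says.** Section 7.1.2 defines seriousness by outcome: "A serious adverse event (SAE) is any adverse event, regardless of causality, that results in ANY of the following outcomes". Whether an event is expected plays no part in the definition.

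Section 7.2 is the adverse event list for the agent, introduced with "Thus, BVD-523's risk profile may potentially include the following". It is a narrative that mixes animal findings, effects of other drugs on the same pathway, and some early clinical experience with BVD-523. Under gastrointestinal toxicity it describes one phase 1 patient who had an SAE of renal insufficiency following dehydration.

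Section 7.3, under the label "For expedited reporting purposes only", has two bullets. The first says that AEs in the agent's list above "should be reported only if the adverse event varies in nature, intensity or frequency from the expected toxicity information which is provided". The second says that other events not needing expedited reporting are set out in the next section, under a sub-heading for protocol-specific exclusions.

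Section 7.4.1 obliges investigators to report any SAE from first dose to 30 days after last dose to the Overall PI, "no later than 24 hours of the investigator learning of the SAE". Section 7.4.2 asks that the same SAEs go to the drug supplier and states no time limit. Section 7.4.3 sends AEs to the IRB office under that office's own policy.

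Section 7.6 requires every AE, expedited or not, in routine data submissions to the Overall PI. Section 7.7 makes the Overall PI, as sponsor, responsible for all FDA communication.

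**The concern.** A site with a serious event that fits the 7.2 description finds one section telling it not to expedite and the next telling it to report within 24 hours. If it follows 7.3, the Overall PI learns of the event from routine forms, and the protocol gives no interval for submitting those. The Overall PI is also the sponsor and the only route to the FDA, so any expedited report to the FDA can start only once the site has told the Overall PI.

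The sponsor normally judges expectedness, with all the data on the drug in view. Section 7.3 as written gives that judgement to the site, before the sponsor has heard of the case. The information that section 12.2 says the DSMC may receive includes unexpected AEs of grade 2 or higher, so that review is not a sure substitute for a listed event.

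**Working it through.** The protocol states no figure on this point, so there is none to reproduce. The check is a side-by-side reading.

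1. **Which events does the 7.3 filter cover?** It refers to events listed above. The list that precedes it is 7.2, so the filter covers the 7.2 effects.

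2. **Does it reach serious events?** Nothing in the bullet excludes them, and under 7.1.2 an SAE is a kind of AE. The site's expedited duties to the Overall PI and the supplier (7.4.1, 7.4.2) concern only SAEs. Applied to those two routes, the filter can act only on serious events.

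3. **Does 7.4 give way to the filter?** No. Neither 7.4.1 nor 7.4.2 has an exception for expected or listed events.

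4. **Is there text that settles the scope?** The second 7.3 bullet speaks of *other* events that need no expedited reporting. This implies that events caught by the first bullet need none either. It then points to exclusions in 7.4. Section 7.4 consists of 7.4.1, 7.4.2 and 7.4.3, and none contains such a sub-heading.

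5. **Test case: a hospitalisation for renal insufficiency caused by dehydration.** Section 7.2 already describes this event as an SAE, so a recurrence matches the list in nature and, if similar, in intensity. For frequency, 7.2 offers one case among the first 18 phase 1 patients, 1/18 = 5.6%. One case in a full trial of 25 would be 1/25 = 4.0%, which is not higher. One case among the 13 first-stage patients would be 1/13 = 7.7%, but a single event against a single event cannot establish a difference. On its ordinary reading the event does not vary from what is provided. The instructions are then:
   - 7.3: do not expedite.
   - 7.4.1: report to the Overall PI within 24 hours.
   - 7.4.2: report to the supplier, no time limit stated.
   - 7.6: enter on the routine form.

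The first instruction contradicts the second and third. The fourth means that the event is recorded in any case.

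**The case against.** The strongest reply is that the sections can be read together. Section 7.4.1 is an unconditional obligation, specific to SAEs, in the section that sets expedited duties. Section 7.3 uses the weaker *should*, speaks of AEs, and stands in a section on describing events. An expectedness filter would also fit the IRB route in 7.4.3, which concerns AEs. Many sites would simply follow 7.4.1. This stands as far as it goes, and it is why the conflict is a risk and not a demonstrated gap. But the protocol nowhere limits the filter to that route or to non-serious events, and the text that might have done so is missing.

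Some stronger readings are tempting, and the documents do not support them.

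- A reader might infer that such events go *unreported*. Section 7.6 rules that out; they may fail to be expedited.
- A reader might infer that first human cases of class effects would be held back, since 7.2 notes that "clinical studies of MEK1/2 kinase inhibitors highlight ocular toxicities". For BVD-523 itself, 7.2 reports no exposure-dependent eye toxicity in animals and a single AE of vision changes in a patient. A retinal vein occlusion could fairly be said to vary from that, and so be reportable under 7.3 itself. Nor can one say that an effect has never been seen with BVD-523: 7.2 is a short summary that defers to the Investigator's Brochure, and its human data cover the first 18 patients or run to 1 April 2014.
- For the same reason the conflict cannot be said to cover every risk category in 7.2. It is clear mainly for effects 7.2 reports in patients: skin, photosensitivity and gastrointestinal.
- A reader might put the delay at about three months from the DSMC schedule. Section 12.2 allows up to four reviews a year or more often if required, and 7.6 goes to the Overall PI directly, so no such figure follows.
- A reader might see a second contradiction in 7.2 listing "Death due to disease progression" among events that are not SAEs. That is an explicit exclusion, consistent with section 13.6, which tabulates deaths reportable as SAEs. Changing it would be a preference.

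**Conclusion.** The point holds as an internal contradiction that should be corrected. For a serious event matching its 7.2 description, 7.3 and 7.4 give opposite instructions to the site, and the missing exclusions list leaves the intended scope open. The possible consequence is loss of the 24-hour notice to the Overall PI, and with it of timely sponsor assessment for FDA reporting. The event still reaches the data through 7.6.

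No numerical size can be given, because the protocol states neither a submission interval for routine forms nor expected rates for most listed events. The primary endpoint, the two-stage rule and the sample size are unaffected. The conclusion assumes that the 7.3 reference to listed events means 7.2, and that no exclusions list exists in a part of the protocol not available for review.

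**What to change.** Make three wording changes.

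1. In 7.4, state that 7.4.1 and 7.4.2 apply to every SAE, whether or not it is listed or expected. The definition in 7.1.2, with the stated exclusions in 7.2, stays as it is.
2. Delete the first expedited-reporting bullet in 7.3, or limit it expressly to the sponsor's own expectedness assessment under 7.7.
3. Remove the 7.3 pointer to the exclusions sub-heading that 7.4 does not contain.

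The cost is a protocol wording change and, at sites that would have applied the filter, a few more SAE forms in a trial of at most 25 patients. No analysis changes.

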7.4 Expedited Adverse Event Reporting

7.4.1 Investigators **must** report to the Overall PI any serious adverse event (SAE) that occurs after the first dose of study treatment, during treatment, or within 30 days of the last dose of treatment on the local institutional SAE form. Study personnel must alert the Overall PI as soon as possible (**no later than 24 hours of the investigator learning of the SAE**).

7.4.2 Any serious adverse event (SAE) that occurs after the first dose of study treatment, during treatment, or within 30 days of the last dose of treatment should also be reported to BVD via Clinipace using the local institutional SAE form. Please include [name] ([contact]), [name] ([contact]) and [name] ([contact]) on all emails that are sent to Clinipace ([contact]) regarding SAEs.

7.4.3 DF/HCC Expedited Reporting Guidelines

Investigative sites within DF/HCC will report AEs directly to the DFCI Office for Human Research Studies (OHRS) per the DFCI IRB reporting policy.

7.5 Expedited Reporting to Hospital Risk Management

Participating investigators will report to their local Risk Management office any participant safety reports or sentinel events that require reporting according to institutional policy.

7.6 Routine Adverse Event Reporting

All Adverse Events **must** be reported in routine study data submissions to the Overall PI on the toxicity case report forms. **AEs reported through expedited processes (e.g., reported to the IRB, FDA, etc.) must also be reported in routine study data submissions.**

7.7 Expedited Reporting to the Food and Drug Administration (FDA)

The Overall PI, as study sponsor, will be responsible for all communications with the FDA. The Overall PI will report to the FDA, regardless of the site of occurrence, any serious adverse event that meets the FDA's criteria for expedited reporting following the reporting requirements and timelines set by the FDA.

PHARMACEUTICAL INFORMATION

A list of the adverse events and potential risks associated with the investigational agent administered in this study can be found in Section 7.2.

8.1 BVD-523

8.1.1 Description

When BVD-523 was characterized using *in vitro* screens against 66 receptors and ion channels no toxicologically significant interactions were identified. Additionally, BVD-523 was negative in bacterial mutation and *in vivo* micronucleus screening assays, so BVD-523 is not considered to have a significant genetic toxicology risk.

While BVD-523 modestly inhibits the hERG current (IC₅₀ 3.4 μM), no significant effects were seen in action potentials recorded from dog Purkinje fibers exposed to up to 10 μg/mL, and no significant cardiovascular findings were observed upon acute oral dosing of the compound at dose levels up to 50 mg/kg in dogs (C_{max} = 17.3 μM). Thus BVD-523 is considered to have a low potential to cause QT prolongation in patients, but, as stated, the study will monitor for signs of cardiovascular effects of BVD-523 in humans.

No significant cytochrome P450 (CYP) inhibition has been observed with the compound. *In vitro* studies suggest that the compound is metabolized primarily via oxidation by multiple CYPs, including 3A4, 2D6, and 1A2. Furthermore, no significant CYP induction was observed after up to 14 days drug treatment in rats, nor during *in vitro* studies with human hepatocytes. These data suggest a limited potential for drug-drug interactions.

BVD-523 HCl salt is orally available in multiple species (absolute bioavailability %F = 23% in dog to 100 % in monkey) when formulated as a simple suspension in 1% carboxymethylcellulose (CMC) and has a half-life of 2–4 hours across all species.

BVD-523 was administered to male and female Sprague-Dawley rats in several toxicology studies: a GLP study for up to 28 days at dose levels up to 50 mg/kg/day twice daily; for up to 14 days at dose levels up to 100 mg/kg twice daily; and for up to 5 days at dose levels up to 150 mg/kg/dose once daily. The incidence and severity of mineralization seen in these studies was dose-dependent and effects were observed in 1 or more tissues at toxic doses. In animals in which mineralization occurred after treatment with BVD-523, significantly increased serum phosphorus and modestly decreased serum calcium were seen; these effects were not observed in animals in which there was no mineralization. Therefore, the risk of tissue mineralization can be assessed by serum phosphorus and calcium monitoring. A

clinical monitoring strategy similar to this was previously employed for related drugs that target the MAPK pathway because those compounds likewise elicited mineralization in rodents.

When BVD-523 was administered to male and female Sprague-Dawley rats for up to 28 days at a dose level of 25 or 50 mg/kg twice daily, it was poorly tolerated. Although most clinical signs and clinical pathology findings reversed following 4 weeks of recovery, skin lesions and histopathology findings persisted in many tissues at both dose levels after the recovery phase. Based on these findings, 25 and 50 mg/kg twice daily dose levels were considered severely toxic. Administration of 12.5 mg/kg twice daily for 28 days was generally welltolerated by rats of both sexes; however, this dose level was associated with test articlerelated findings that included: swelling in the neck; decreased forelimb strength; multiple clinical pathology findings; enlarged lymph nodes, spleen, and mammary gland. Based on these findings, the severely toxic dose in 10% of the animals (STD10) for BVD-523 when administered for up to 28 days in Sprague-Dawley rats is 12.5 mg/kg given twice daily (25 mg/kg/day). On Day 28 of the dosing phase, this dose level corresponded with a Cmax of 28700 and 15323 ng/mL and AUC0-12 of 264868 and 124341 hr.ng/mL for males and females, respectively.

BVD-523 was administered to male and female beagle dogs for up to 28 days at dose levels of 15, 5, or 2 mg/kg twice daily. Initial analysis of the toxicity profile observed shows that BVD-523 was well tolerated in dogs. The rat was designated the most sensitive species and rat data were used to calculate the starting dose in man.

BVD-523 has a measured UV absorbance at 320 nm, which means that it can absorb both UV-A and UV-B. BVD-523 may therefore act as a photosensitizing agent in man. Based on the data accumulated to date, BVD-523 possesses a toxicology profile which presents no impediment to its development as an anti-cancer agent.

For further information, please refer to the BVD-523 Investigator's Brochure.

